8.3.7. Electrocardiograms

12-lead ECGs will be performed at screening, Cycle 1 Day 8, 15 and 22, Day 1 of each subsequent even cycle (Cycle 2, 4, 6, ...) and the end of treatment visit.

Three serial ECGs will be conducted within approximately 5 to 10 minutes total time. 12-lead ECGs should be preceded by at least 5 minutes of rest for the participant in a quiet setting without

distractions (e.g. television, cell phones) after the participants has rested in the supine position for at least 5 minutes:

12-lead ECGs will be performed before blood collection, where applicable.

Interpretation of the tracing will be made by a qualified physician and documented in the eCRF. QT interval values will be corrected for pulse rate using the Fridericia formula (QTcF). Clinically significant abnormalities present at screening but prior to the first dose of study treatment should be recorded as medical history in the eCRF.

An abnormal 12-lead ECG (e.g. QTcF of >500 ms or with a change in QTcF from baseline of ≥ 60 ms) may be repeated if it cannot be interpreted by the investigator. ECG tracings will be made available if requested by the sponsor.

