
[i] Clinical chemistry: Albumin, alkaline phosphatase, ALT, AST, total bilirubin (and direct bilirubin), BUN/urea, calcium, chloride, CK, creatinine, GGT, glucose, LDH, lipase and amylase, magnesium, phosphate, potassium, sodium, total protein, troponin I or T, uric acid. These tests will be done under fasting conditions.
 
[j] Coagulation: PT, INR, aPTT
 
[k] Urinalysis tests: appearance, colour, specific gravity, pH, protein, glucose, ketones, blood, nitrites, leukocytes
 
[l] Hepatitis B (HBsAg, HBsAg antibody, hepatitis B core antibody and HBV DNA if HBsAg or HBcAb is positive), hepatitis C antibody, HIV
 
[m] Pregnancy test
 
At baseline and EOT visit serum β-HCG for women of childbearing potential only
 
During treatment phase urine pregnancy test for women of childbearing potential only
 
[n] Tumor assessment (MRI or CT scan): Tumor overall assessment (response, stable disease, progressive disease) will be determined locally by the investigator and reported in the eCRF along with the date of the radiological assessment.
 
During treatment phase radiological assessments should be performed at least every two cycles (8 weeks) ± 7 days for the first 12 months, then at least every three cycles (12 weeks) ± 7 days until disease progression. More frequent radiological assessments may be performed if needed.
 
At EOT visit if the previous tumor assessment has been performed less than 30 days, there is no need to repeat the tumor assessment.
 
[o] ECG: three serial ECGs conducted within approximately 5 to 10 minutes total time after at least 5 minutes rest. When an ECG is to be performed at the same time point as a blood collection, the ECG should be performed first.
 
[p] Serial PK sampling will be collected at pre-dose, and 1, 2, 4, 6 hours post-dose on Cycle 1 Day 1 and Cycle 2 Day 1 only
												

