5.1. General Considerations

All analyses will be performed using the SAF otherwise specified. Individual data will be listed on specific population as specified in the list of TFLs. In SAF and PK listings, participants excluded from DDS will be flagged (*).

Statistical analysis will be performed after database lock or data snapshot (see Protocol Section 10.1.8.3.5), using statistical analysis software (SAS[®]) Version 9.4 or higher.

In general, following descriptive methods will be used to present all relevant data:

- Continuous data will be presented using number of observations, number of missing (if any), mean, standard deviations, median, Q1, Q3, minimum and maximum. 95% Confidence Intervals (CI) will be presented if relevant.
- Categorical data will be summarized using number of observations, frequencies, percentages and number of missing (if any missing). Unless otherwise specified, the calculation of proportions will be based on the non-missing data. Counts of missing observations will be excluded from the denominator.

Baseline is defined as the last completed and available assessment prior to date of first dose of study treatment (including unscheduled or re-test). If an assessment that is planned to be performed prior to the first dose of study treatment in the protocol is performed on the same day as the first dose of treatment and the time is unknown, it will be assumed that it was performed prior to study treatment administration and will be considered as baseline assessment.

Unscheduled assessments will be used in the determination of baseline. Data reported at the end of treatment visit are not eligible for baseline selection.

ECG Baseline will be the mean of the last triplicate measurements performed before the first study treatment administration (i.e. screening assessment per Table 3 Schedule of Activities). If no triplicate available, then baseline will be the last single ECG measurement performed before the first study treatment administration. For the interpretation parameter (normal/abnormal and its related clinical significance), the baseline will be the last completed and available assessment performed before the first study treatment administration, regardless triplicate or single ECG.

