For summary statistics by visit, only scheduled visits will be summarized. Re-test and unscheduled assessments will not be taken into account for summaries of post-baseline visit. For analyses of worst post-baseline assessment, all on-treatment values are considered regardless scheduled or unscheduled. For visits where triplicate ECG are collected, value of numeric parameters will be the average, and value of interpretation will be last non-missing record (ie both interpretation and clinical significance if abnormal should be non-missing).

For TFLs, visits will be identified as collected in CRF.

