5.6.6. ECG

12-lead ECGs will be performed at screening, Cycle 1 Day 8, 15 and 22, Day 1 of each subsequent even cycle (Cycle 2, 4, 6, ...) and the end of treatment visit.

12-lead ECGs will be performed before blood collection, where applicable.

For a given parameter at a given post-baseline visit, mean of the results at the available timepoints will be used for summary statistics.

ECG parameters will be described at each scheduled visit and listed in participants from the SAF, with a flag for clinically notable values.

Frequency counts and percentages of participants having at least one post-baseline clinically notable ECG values during study (Table 6) will also be described.

Table 6: Clinical Notable ECG Criteria

Parameter	Criterion
QT, QTcF	increase from baseline > 30 ms increase from baseline > 60 ms new > 450 ms new > 480 ms new > 500 ms
Heart rate	Increase from baseline $> 25\%$ to a value > 100 bpm Decrease from baseline $> 25\%$ and to a value < 50 bpm

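### At triplicate ECG visits the SAP keeps the last complete interpretation, so a clinically significant earlier tracing can appear in the by-visit summary as normal or not significant

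*SAP*

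**What the plan says.** Each ECG assessment consists of "three serial ECGs conducted within approximately 5 to 10 minutes total time after at least 5 minutes rest" (SAP 1.2.1, Schedule of Activities). On reading them, Protocol 8.3.7 states: "Interpretation of the tracing will be made by a qualified physician and documented in the eCRF".

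SAP 5.1 reduces the three tracings to one visit result: "value of numeric parameters will be the average, and value of interpretation will be last non-missing record". It then defines non-missing: "ie both interpretation and clinical significance if abnormal should be non-missing". For baseline interpretation, "the baseline will be the last completed and available assessment performed before the first study treatment administration, regardless triplicate or single ECG".

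On outputs, SAP 5.6.6 says "ECG parameters will be described at each scheduled visit and listed in participants from the SAF, with a flag for clinically notable values". For post-baseline numeric results, "mean of the results at the available timepoints will be used for summary statistics". The clinically notable criteria in SAP Table 6 are numeric and cover only QT, QTcF and heart rate. SAP 5.1 adds that "For analyses of worst post-baseline assessment, all on-treatment values are considered regardless scheduled or unscheduled", but SAP 5.6.6 specifies no worst-value analysis of ECG interpretation.

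**The concern.** The averaged numeric parameters use all three tracings. The interpretation uses one, picked because it came last and was complete. Within a 5 to 10 minute series, the last tracing has no better claim than the others to represent the visit.

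The completeness condition also treats normal and abnormal records differently. A normal record needs only an interpretation. An abnormal record needs a significance entry as well. So only abnormal records can be set aside for a blank significance field, and the visit then shows no missing value.

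ECG change is a named secondary endpoint. An abnormality that is not a matter of QT, QTcF or heart rate reaches the ECG tables only through the interpretation field. If that field is understated, no other ECG table corrects it. With three to six evaluable participants, one participant is 1/3 = 33.3 or 1/6 = 16.7 percentage points of a by-visit percentage. A single reclassified visit would be visible.

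**Working it through.** The plan gives no figure to reproduce, so the check applies the rule to every possible triplicate.

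**Inputs.** Three tracings per visit (SAP 1.2.1). Each is normal (N), abnormal not clinically significant (NCS), abnormal clinically significant (CS), or missing/incomplete (M). M includes an abnormal tracing with significance blank, because SAP 5.1 does not count that as non-missing. SAP rule: take the last record that is not M. Comparator: take the worst record.

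**Complete triplicates with CS on tracing 1 or 2.**
- All patterns: 3 × 3 × 3 = 27. With no CS on tracings 1 and 2: 2 × 2 × 3 = 12. Remaining: 27 − 12 = 15.
- For each value of tracing 3 there are 9 − 4 = 5 qualifying pairs on tracings 1 and 2.
- SAP rule: N in 5, NCS in 5, CS in 5. Severity is understated in 10 of 15.
- Worst-of-triplicate: CS in 15 of 15.

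**Allowing missing or incomplete records.**
- 4 × 4 × 4 = 64; with no CS on tracings 1 and 2: 3 × 3 × 4 = 36. Remaining: 28.
- Tracing 3 complete: 16 − 9 = 7 patterns for each of N, NCS and CS.
- Tracing 3 is M: 7 patterns. The rule falls back to tracing 2, or to tracing 1 if that is also M, giving N in 1, NCS in 1 and CS in 5.
- SAP rule in total: N 7 + 1 = 8, NCS 7 + 1 = 8, CS 7 + 5 = 12. Worst-of-triplicate: CS in 28 of 28.

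**Examples.**

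| Tracings 1, 2, 3 | SAP rule | Worst of three |
|---|---|---|
| CS, N, N | N | CS |
| N, CS, N | N | CS |
| CS, CS, N | N | CS |
| CS, N, CS | CS | CS |
| N, N, abnormal with significance blank | N | abnormal, significance missing |
| CS, CS, abnormal with significance blank | CS | CS |

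The last two rows show that the completeness condition can hide an abnormality or preserve an earlier one, depending on what came before.

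**Random-order illustration (an assumption; the documents give no rate of disagreement between tracings).** With one abnormal tracing in three, P(last is normal) = 2/3 = 67%. With two in three it is 1/3 = 33%. The visit is therefore shown as abnormal with probability 1/3 or 2/3, which is exactly the share of tracings that are abnormal.

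**The case against.** The strongest reply is that this is a display convention with little reach, and much of that stands.

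- **Not every early abnormality is lost.** A reader might infer that a significant finding on tracing 1 or 2 is always reported as normal. It is not: the last complete record may itself be significant or not significant, and it need not be the third tracing.
- **No bias in absolute terms.** A reader might infer that counts of abnormal ECGs are biased downwards. Under random order the rule reproduces the share of abnormal tracings. It is low only against a worst-of-three standard, which the SAP does not adopt for ECGs.
- **QT safety is untouched.** A reader might link the rule to QT prolongation, an important risk and an event of special interest. The QT and QTcF counts in Table 6 are numeric, and events of special interest are retrieved from adverse event data (SAP 5.6.2 and 6.12). Neither uses the interpretation field.
- **The finding is captured elsewhere.** ECG results that the investigator judges clinically significant meet the adverse event definition (Protocol 10.8.1), and all data are listed (Protocol 9.4.1). With so few participants the listings can be read one by one.
- **Dependence on the eCRF.** The protocol does not say whether interpretation is recorded per tracing or once per triplicate. If once, the rule has no effect.
- **Blank significance fields can be queried.** Data cleaning before lock may remove most of them.

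These points limit the size of the problem but do not make the by-visit summary right. A table could show normal where the listing or the adverse event record shows a significant abnormality. A rule about the last record of a triplicate also makes sense only if a triplicate can hold more than one record. Elsewhere the SAP uses the worst case: maximum laboratory grade (5.6.3.1 and 5.6.3.2), worst blood-pressure grade (5.6.5), worst ECOG status (5.6.8) and worst adverse event grade (5.6.2). It gives no reason for treating ECG interpretation differently.

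**Conclusion.** The point holds as a minor one. The last-complete-record rule can turn a triplicate containing a clinically significant tracing into a normal or not-significant visit, even when two of the three tracings are significant. It can also replace an abnormal tracing lacking a significance entry with an earlier normal one. Over complete patterns with a significant abnormality on tracing 1 or 2, severity is understated in 10 of 15. How often this would happen in practice cannot be estimated from the documents.

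The consequence stops at the by-visit interpretation summary. The primary endpoint, the Trial Steering Committee's tolerability criteria, the Table 6 counts, adverse events, events of special interest and listings do not depend on it. The documents do not support a claim that a safety signal is lost or that QT findings are understated.

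The conclusion rests on two assumptions: that interpretation is recorded per tracing, and that interpretation is among the ECG parameters tabulated by visit. SAP 5.1 treats it as a parameter, but the table shells are in a separate document, and SAP 6.2 allows some summaries to be replaced by listings.

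**What to change.** In SAP 5.1, define the interpretation at a triplicate visit as the worst across the tracings, in the order: abnormal clinically significant, abnormal with significance missing, abnormal not clinically significant, normal. Keep means for numeric parameters.

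Apply the same rule at baseline, to the last pre-dose triplicate. Changing only the post-baseline rule would compare the worst of three readings on treatment with a single last reading before it, and would inflate apparent worsening even with no drug effect.

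The cost is a short edit to two rules in SAP 5.1 and one sort order in programming. The downside is that slightly more visits, at baseline and after, will be shown as abnormal. If the eCRF holds one interpretation per triplicate, the edit changes no result. If the sponsor prefers the last-record rule, the SAP should give the reason.

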5.2. Participant Dispositions

Participant dispositions will be summarized with number and percentage of participants:

- screened;
- screened failure;
- included in each study population (analysis set);
- reason for treatment discontinuation.
- treatment discontinuation due to DLT during DLT evaluation period

Data will also be listed.

In addition, data collected in the CRF form “Covid-19 Impact” will be listed. Summary of Covid-19 (SARS-CoV-2) impact will be provided with number and percentages of participants impacted by: Visit, Case Report Form, Category.

A summary table will be provided for:

- Treatment discontinuations related to Covid-19 (SARS-CoV-2): This will be defined as an event reported in “Covid-19 impact form” having CRF form entered as “Disposition - End of Treatment” and visit name entered as “End of Treatment”. It will be presented overall and by reason for treatment discontinuation
- Missed visit due to Covid-19 (SARS-CoV-2), overall and by visit label: This will be defined as a visit not performed with reason verbatim containing “COVID-19”.

5.3. Primary Endpoint(s) Analysis

The primary endpoint is the incidence of DLTs experienced during Cycle 1 (Days 1 to 28) of encorafenib treatment.

5.3.1. Definition of Endpoint(s)

A DLT is defined as any adverse event or abnormal laboratory value assessed as unrelated to disease, disease progression, intercurrent illness or concomitant medications/therapies that satisfies at least one of the criteria listed in Table 2 (see Section 1.2).

DLTs will be identified using the DLT flag reported in the Adverse Event CRF form.

5.3.2. Main Analytical Approach

The occurrence of DLTs will be summarized descriptively for the DDS:

- The number and proportion of participants experiencing DLTs during the DLT evaluation period (defined as the first 28 days after the first dose of study intervention, i.e. from Day 1 to Day 28 inclusive)
- The number and proportion by Type of DLT, by Preferred Term, by Grade, by Action Taken.

All reported DLT will be listed for the DDS, including also any DLT occurring outside of DLT evaluation period (i.e. prior to encorafenib first intake or posterior to Day 28).

5.3.3. Sensitivity Analysis

Not Applicable

5.3.4. Supplementary Analyses

Not Applicable

5.4. Secondary Endpoint(s) Analysis

The secondary endpoints are:

- Incidence, nature and severity of TEAE graded as per NCI CTCAE Version 4.03, TEAEs leading to dose interruption, reduction and discontinuation, treatment-emergent Serious Adverse Events (SAEs) and deaths
- Changes clinical laboratory parameters, vital signs, ECGs
- Incidence of targeted TEAEs of special interest
- Dermatological examinations
- Performance status using the ECOG performance status scale
- PK parameters of encorafenib and its metabolite (LHY746) after single and repeated administration

5.4.1. Key Secondary Endpoint(s)

5.4.1.1. Definition of Endpoint(s)

- Grades of clinical safety laboratory assessments will be derived using NCI CTCAE Version 4.03.
- For vital signs, changes from baseline of continuous endpoints (SBP/ DBP/Temperature/ Pulse rate/ Respiratory rate) will be derived: Value at the visit – Value at baseline.
- For all other endpoints, raw values will be used.

5.4.1.2. Main Analytical Approach.

Secondary PK endpoints are described and will be analyzed as specified in Section 5.7.1.1.

Method for analysis of safety endpoints is detailed in Section 5.6.

5.4.1.3. Sensitivity Analysis

Not applicable

5.4.1.4. Supplementary Analyses

Not Applicable.

5.4.2. Supportive Secondary Endpoint(s)

Not Applicable.

5.5. Tertiary/Exploratory Endpoint(s) Analysis

5.5.1. Scan Assessment

Listing of all tumor assessments performed during the study will be provided with dates and responses determined according to RECIST version 1.1.

In addition, listings of target lesions, non-target lesions and new lesions will also be provided.

5.6. (Other) Safety Analyses

5.6.1. Study Intervention Exposure

The study intervention is the encorafenib, administrated daily.

Exposure to the encorafenib is defined as the time interval in days between the actual date of first encorafenib administration (included) and the actual date of last encorafenib administration (included), derived as:

[Date of last dose of encorafenib or date of cutoff*] – [date of first (non-zero) dose of encorafenib] + 1.

* If participant is off treatment, this is the last non-zero dose of the study drug. If the participant is on treatment at the cutoff date, this is the cutoff date.

The duration of exposure will also be computed in weeks (dividing by 7 the above computation) with one decimal place, and summarized in participants from the SAF for following variables:

- Duration as continuous (in weeks) using descriptive statistics
- Categorized by time intervals (< 4 weeks, 4-<8 weeks, ...) for which frequency counts and percentages of participants will be provided

Total subject time, expressed in patient-months, will be provided in participants from the SAF. Total subject time will be a unique number, calculated as the sum of the duration of encorafenib exposure (in days) for each participant divided by 30.4375. The total subject time (aside the number of participants) will be provided according to:

- The duration of encorafenib exposure (i.e. for participants with at least 1, 3, 6 or 12 months of encorafenib exposure)
- The age group as per Risk Management Plan (18 - 64 years, 65 - 74 years, 75 - 84 years, 85+ years and, Total) cross tabulated with sex (Female vs Male).

The actual Dose Intensity (DI) and Relative Dose Intensity (RDI) will be defined for encorafenib as below.

Sponsor Name: Pierre Fabre Médicament

Sponsor Protocol ID: W00090GE102

PII

The actual Dose intensity (DI) will be defined as DI (mg/day) = Cumulative actual dose/duration of planned exposure in days as computed above.

The RDI is defined as:

$$\text{RDI (\%)} = (\text{DI}/\text{PDI}) * 100$$

where:

- DI is the dose intensity as defined above,
- PDI is the Planned Dose Intensity during the study for encorafenib, i.e. 300 mg/day.

Actual DI and RDI will be calculated with no more than one decimal.

Actual DI and RDI (%) will be summarized in participants from the SAF. Descriptive statistics will be provided. For RDI, number and percentage of participants will be provided for following categories: <50%, 50 - <80%, 80 - <100%, 100%, >100%.

In addition, the RDI specific to Cycle 1 will be defined as 100*administered dose (mg) through Cycle 1 divided by planned dose (mg), with planned dose being 8400 mg for encorafenib (28 daily doses of 300 mg).

Relative dose intensity in Cycle 1 will be listed in the listing of dose intensities.

Dose modifications will be defined as below:

- A dose interruption will be indicated in the eCRF by a dosing record with a total daily dose of 0 mg for one or more days.

To avoid over-counting interruptions, dosing records with 0 mg entered as last dosing record will not be counted as interruptions. Those represent the reason for permanent discontinuation and will therefore be presented in the reason for treatment permanent discontinuation analysis.

- A dose reduction is defined as a decrease in dose from the protocol-planned dose and a decrease from the previous non-zero dose, even if this decrease has been directly preceded by an interruption. For example, for encorafenib, in the sequence of total daily dose 300 mg – 0 mg – 200 mg, the 200 mg dose will be counted as a reduction.

If a participant moves from a higher than protocol-planned dose down to the planned dose then this is not to be counted as a reduction, however if they move directly from a higher than planned dose down to a lower than protocol-planned dose or the planned dose on a less frequent regimen, then this is counted as a reduction.

If the dose on the first dosing record is lower than protocol-planned dose this is also counted as a reduction.

Frequency counts and percentages of participants who have dose reductions or interruptions, and corresponding reasons, will be summarized for participants from the SAF. Dose reductions and interruptions will be tabulated both separately and in a combined fashion.

Sponsor Name: Pierre Fabre Médicament

Sponsor Protocol ID: W00090GE102

PII

For participants with dose reduction as defined above, the percentages of days between the first and last non-zero dose with reduced dose i.e., below the protocol-planned dose will be summarized and specified in the related listing. Note, in this calculation a dose of 0 mg will also be considered a reduced dose.

For participants with dose interruption as defined above, the percentages of days with dose interruption will also be summarized and specified in the related listing.

Treatment interruptions due to Covid-19 (SARS-CoV-2) will be described as part of the data collected by the “Covid-19 impact” CRF form. Information about administration and exposure of encorafenib will be presented in data listings, with duration of exposure presented in days.

A listing of drug accountability will also be provided.

